9.1.2 Analyses for Categorical Efficacy End Points

All ordinally scaled categorical data will be analyzed using CMH test with modified ridit scores which make no assumptions regarding scaling of response level other than that implied by relative ordering. Frequency tables and the CMH test will be applied to the actual value of each visit a variable is measured.

9.1.3 Analyses for Binary End points

Not applicable in current SAP.

9.1.4 Analyses for Biomarkers

Biomarkers with baseline and post-baseline data will be analyzed in the same way as the other efficacy end points using the ANCOVA model with adjustment for age, AD severity, and the baseline value. The biomarkers will also be analyzed by AD severity. The biomarkers assessed by different methods will be analyzed by assessment method.

	Title: Statistical Analysis Plan
	Project #: IG1002 AMBAR
	Version: Final 1.0 Effective Date: 31July2018 Protocol Version: Version 5.0 Effective Date: Feb2018

9.1.5 Analyses for Safety

All analysis of safety will be descriptive statistics. For laboratory values, summary statistics for the actual value and for the change from baseline will be provided. Adverse events will be summarized by frequency counts and percentages.

9.2 STATISTICAL ANALYSES

9.2.1 Primary Analysis

The primary analysis is based on the FAS population and the primary end points of 1) change from baseline in the Total ADAS-Cog change from baseline score and 2) change from baseline in the ADCS-ADL inventory score at month 14 using MMRM as described in Section 9.1.1 above.

To support the interpretation of the primary analysis, an identical analysis as described above, based upon the PP population rather than the FAS, will be conducted.

The co-primary end points ADAS-Cog and ADCS-ADL will also be analyzed by AD severity as defined in Section 7.4. The same primary analysis will be performed as for the entire population with the exception that the MMRM will not be adjusted for AD severity.

9.2.2 Secondary Analyses

All other efficacy analyses are considered secondary. Basic descriptions of the end points can be found in Section 7.1. For a full list of secondary analyses, please see Section 9.2.4.

9.2.3 Safety Analyses

All safety analyses are descriptive with no inferential statistics. Descriptions of the safety end points and their proposed analysis can be found in Section 7.2.

9.2.4 Analysis of Biomarkers

Analysis of biomarkers will be performed as described in Section 9.1.4.

	Title: Statistical Analysis Plan
	Project #: IG1002 AMBAR
	Version: Final 1.0 Effective Date: 31July2018
	Protocol Version: Version 5.0 Effective Date: Feb2018

9.2.5 Summary of Efficacy Analyses

End point	Analysis Set	Statistical Method	Model/ Covariates	Missing Data	Interpretation/Comments
Total ADAS-Cog at Month 14	FAS	MMRM	Treatment/Week Bsl/Age/AD severity	Uses all non-missing data	Co-Primary Analysis
	PP	MMRM	Treatment/Week/Bsl/Age/AD Severity	Uses all non-missing data	Check for robustness of primary analysis
	FAS	ANCOVA	Treatment/Bsl/Age /AD Severity	Excluded	Sensitivity analysis
	FAS	ANCOVA	Treatment/Bsl/Age /AD Severity	LOCF	Check for impact of missing data on standard ANCOVA models.
	FAS	Random Slope Model	Treatment/Time/ Bsl/Age/AD Severity	Uses all non-missing data	Sensitivity analysis
Total ADAS-Cog at Time Points	FAS	ANCOVA	Treatment/Bsl/Age /AD Severity	Excluded	Secondary analysis of investigation of time course of efficacy
Total ADCS-ADL at Month 14	FAS	MMRM	Treatment/Week Bsl/Age/AD Severity	Uses all non-missing data	Co-Primary Analysis
	PP	MMRM	Treatment/Week/Bsl/Age/AD Severity	Uses all non-missing data	Check for robustness of primary analysis
	FAS	ANCOVA	Treatment/Bsl/Age /AD Severity	Excluded	Sensitivity analysis

	Title: Statistical Analysis Plan
	Project #: IG1002 AMBAR
	Version: Final 1.0 Effective Date: 31July2018
	Protocol Version: Version 5.0 Effective Date: Feb2018

	FAS	ANCOVA	Treatment/Bsl	LOCF	Check for impact of missing data on standard ANCOVA models.
	FAS	Random Slope Model	Treatment/Time/Bsl/Age/AD Severity	Uses all non-missing data	Sensitivity analysis
Total ADCS-ADL at Time Points	FAS	ANCOVA	Treatment/Bsl/Age /AD Severity	Excluded	Secondary analysis of investigation of time course of efficacy
ADAS-Cog domains at Time Points (12 domains)	FAS	ANCOVA	Treatment/Bsl/Age /AD Severity	Excluded	Secondary analysis of ADAS-Cog domains
MMSE at Time Points	FAS	ANCOVA	Treatment/Bsl/Age /AD Severity	Excluded	Secondary analysis of cognitive impairment
Neuropsychological Specific battery (NPSB) with it's components RAVLT (5 scores), NAB naming test (1 score), SDTM (1 score), Phonetic and semantic fluency (2 scores) CSDD (1 score) at Time Points	FAS	ANCOVA	Treatment/Bsl/Age /AD Severity	Excluded	Secondary analysis of cognitive impairment
Neuropsychiatric inventory questions	FAS	ANCOVA	Treatment/Bsl/Age /AD Severity	Excluded	Secondary analysis of cognitive impairment

	Title: Statistical Analysis Plan
	Project #: IG1002 AMBAR
	Version: Final 1.0 Effective Date: 31July2018
	Protocol Version: Version 5.0 Effective Date: Feb2018

(NPI) (2 total scores)Time Points					
Clinical Dementia Rating CDR-Sb (6 domains)	FAS	CMH test (values on time point)		Excluded	Secondary analysis of cognitive impairment
ADCS –CGIC (1 score)	FAS	CHM test (values on time point)		Excluded	Secondary analysis of cognitive impairment
C-SSRS, suicidal ideation severity (1 score)	FAS	CHM test (values on time point)	Treatment/Bsl/Age /AD Severity	Excluded	Secondary analysis of cognitive impairment
QoL-AD (2 scores)	FAS	ANCOVA	Treatment/Bsl/Age /AD Severity	Excluded	Secondary analysis of cognitive impairment
RUD lite	FAS	Summary statistics for individual items			Descriptive analysis for resource consumptions.
Biomarkers at Time Points	FAS	ANCOVA	Treatment/Bsl/Age /AD Severity	Excluded	Biomarkers as secondary end points.

	Title: Statistical Analysis Plan
	Project #: IG1002 AMBAR
	Version: Final 1.0 Effective Date: 31July2018
	Protocol Version: Version 5.0 Effective Date: Feb2018

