7.4 COVARIATES

For the analysis of the cognitive, functional, and neuropsychiatric scores, the corresponding baseline scores, age, and AD severity will be used as a covariate for each change from baseline model. Disease severity will be defined by the baseline MMSE score as follows:

- MMSE 18 – 21 points
- MMSE 22 – 26 points

An exception is the model for the changes from baseline for the MMSE. This model will only be adjusted for age and the baseline value. Also the models for the subgroups by severity will only be adjusted for age and baseline value.

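### SAP table 9.2.5 drops age and AD severity from the ADCS-ADL LOCF model, so one supplementary missing-data check changes covariates as well as missing-data handling

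*SAP*

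**What the plan says.** SAP 7.4 sets one covariate rule that covers all the clinical scales, whether of cognition, function or neuropsychiatric symptoms. It reads: "the corresponding baseline scores, age, and AD severity will be used as a covariate for each change from baseline model". It allows two departures. One concerns MMSE: "An exception is the model for the changes from baseline for the MMSE", and for that outcome the plan goes on to say "This model will only be adjusted for age and the baseline value". The other is for subgroup analyses ("Also the models for the subgroups by severity will only be adjusted for age and baseline value"). SAP 9.1.1 gives the Month 14 ANCOVA for both co-primaries the same set: baseline, age and AD severity.

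The table in SAP 9.2.5 then lists the model for each analysis. At Month 14 in the FAS, its model and missing-data columns read:

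- ADAS-Cog, LOCF ANCOVA: "Treatment/Bsl/Age /AD Severity LOCF"
- ADCS-ADL, observed-case ANCOVA: "Treatment/Bsl/Age /AD Severity Excluded Sensitivity analysis"
- ADCS-ADL, LOCF ANCOVA: "Treatment/Bsl LOCF"

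Both LOCF rows carry the same comment, "Check for impact of missing data on standard ANCOVA models". The discrepancy is in the ADCS-ADL row only.

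The LOCF analysis appears nowhere in the SAP except in this table. SAP 8 and protocol 10.1.2 both say that missing efficacy values are left missing and not imputed.

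**The concern.** The LOCF row exists to show what missing data do to the standard ANCOVA. That requires a comparison of two fits that differ only in how missing values are handled. For ADCS-ADL, the row as written also removes two covariates, so a gap between the LOCF and observed-case estimates has two possible sources and the table gives no way to separate them. It also means that the two co-primaries, both of which must succeed at a given dose, would be given this check under different models.

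Because the table is the only place where the LOCF run is specified, a programmer has one specific instruction (baseline only) and one general rule (SAP 7.4) that disagree. The analysis is therefore not uniquely pre-specified.

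**Working it through.** **1. Is the row covered by an exception?** SAP 7.4 exempts the MMSE model and the severity-subgroup models. ADCS-ADL in the whole FAS is a functional score and is neither of these. SAP 9.1.1 requires the full covariate set. Table 9.2.5 has 12 ANCOVA rows, and this is the only one without age and AD severity. No text gives a reason.

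**2. Could it be a text-extraction fault?** This is unlikely. The row's method, LOCF and comment cells are intact, and the next rows are complete.

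**3. Inputs for size.** SAP 2.1 gives 78 evaluable subjects per group, an ADCS-ADL SD of 10.0 and a planning difference of 6.69 points. These inputs reproduce the plan's own power statement: a two-sided 5% comparison gives 0.987, against over 98% stated. The documents do not give the variance explained by age and AD severity beyond baseline ADCS-ADL. I take 2% to 10% as an assumption.

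**4. Standard error of a dose-versus-control difference.**

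SE = 10 × sqrt(2/78) = 1.60 points.

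**5. Shift caused by dropping the two covariates, same data and no imputation.** Baseline stays in the model, so R² here is the share of variance explained beyond baseline. SD of shift ≈ sqrt(R²) × SE:

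- R² = 2%: sqrt(0.02) × 1.60 = 0.23 points
- R² = 5%: sqrt(0.05) × 1.60 = 0.36 points
- R² = 10%: sqrt(0.10) × 1.60 = 0.51 points

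A two-arm simulation (4,000 trials, 78 per arm, complete data, baseline in both models) gave SDs of 0.29, 0.41 and 0.54 points, with mean shifts within 0.01 of zero. The simulated SDs are a little larger because the covariate slopes are estimated.

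**6. Precision.** With the covariates in, SE = 1.60 × sqrt(1 − R²), which is 1.59 at 2% and 1.52 at 10%. Without them it stays at 1.60.

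**7. Sensitivity to the sample retained.** LOCF keeps dropouts who have a post-baseline score, so there could be up to 364/4 = 91 per arm. Then SE = 10 × sqrt(2/91) = 1.48, and the SD of the shift runs from sqrt(0.02) × 1.48 = 0.21 to sqrt(0.10) × 1.48 = 0.47 points. The rounded range of 0.2 to 0.5 covers both cases.

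**8. Against the planning effect.** 0.23/6.69 = 3% and 0.51/6.69 = 8%.

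**The case against.** The best answer is that the body text already fixes the model. Section 9.2.5 is a summary, SAP 7.4 and 9.1.1 state the rule, and the short cell may simply be left over from the baseline-only ANCOVA in protocol 10.2.2. That is a plausible origin, and nothing suggests a deliberate choice of a reduced model. It does not fully settle the matter, because 9.1.1 never mentions LOCF and the table row is the only specific instruction for that run.

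The second answer stands. A reader might infer that the missing-data assessment for ADCS-ADL as a whole is compromised. The documents do not support that. SAP 9.1.1 rests the assessment mainly on comparing the MMRM with the observed-case ANCOVA, and both ADCS-ADL rows for that comparison carry the full covariate set. It adds a random slope model and a descriptive comparison of completers with dropouts in each group. None of these is touched by the faulty cell, and no decision rule in SAP 4.2 uses the LOCF result.

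The third answer also stands. The size rests on an assumed R², and the planning SD of 10 is for change scores, not a residual SD after baseline. The documents give no expected gap between LOCF and observed-case estimates, so it cannot be shown that the covariate change would hide or mimic a real missing-data effect. It can only be said that the two sources would be mixed.

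**Conclusion.** The inconsistency is real and confined to one cell. As written, the supplementary LOCF check for ADCS-ADL changes covariates and imputation together, which defeats its stated purpose. The consequence is minor: noise with mean about zero and an SD of roughly 0.2 to 0.5 points, plus a slight loss of precision.

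This assumes an SD of about 10 after baseline adjustment, 78 to 91 subjects per arm, 2% to 10% of variance explained by age and severity beyond baseline, and a LOCF set close enough to the randomised groups for these covariates to balance on average.

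A reader might go further and infer a biased treatment estimate or a threat to the co-primary conclusion. Neither follows: randomisation makes the expected shift about zero, and the primary MMRM, alpha, power and sample size do not depend on this row.

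The MMSE row has a separate slip of the same kind. It lists AD severity, which SAP 7.4 excludes for that model. The effect is negligible and adds no weight to the main point.

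**What to change.** In table 9.2.5, change the ADCS-ADL Month 14 LOCF cell to Treatment/Bsl/Age/AD Severity, matching the ADAS-Cog LOCF row.

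In SAP 9.1.1, add a sentence naming the LOCF ANCOVA as a sensitivity analysis for both co-primaries. In SAP 8, make clear that the no-imputation rule does not apply to that run, so that the text and the table agree.

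For consistency, change the MMSE cell to Treatment/Bsl/Age.

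The cost is two table cells and a sentence or two of text. No new analysis is added, and sample size, power and alpha are unchanged.
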